To address antibody endpoints in Part A, the analysis will descriptively summarize binding response positivity call rates, and test superiority of the frequency of differential memory B cell binding (to wild type vs mutant  $\text{I}\Delta 371$  CH505) and of the magnitude and breadth of the IgG binding Ab response to a panel of gp120 proteins for each of 2 comparisons (Group 1 vs 2, and Group 2 vs 3), using a two- sided Wilcoxon rank sum test with 5%/2 type-I error rate per comparison. The sample size of 12 vaccinees per group will give 80% power to detect a true difference of 1.81 standard deviations (SDs) between the mean responses and 90% power to detect a true difference of 2.04 SDs. Using the mean and SD values from the HVTN 088 trial, the difference of 1.81 SDs translates to a difference of 0.708 units of  $\log_{10}$  binding magnitude; if 1 of the comparison groups has the same mean as was seen among non-negative values among vaccine recipients in the HVTN 088 trial (4.06 units), then after incorporating the expected 6% zero-valued (negative responder) measures, this corresponds to observing an increase or decrease in the overall mean from 3.691 in group 1 to 4.336 in group 2. These calculations assume a 10% loss-to-follow-up rate and the (94%) response rate observed in the HVTN 088 vaccine recipients. The same approach will be used to test superiority of the magnitude of the IgG binding Ab response to each individual gp120 antigen in the panel.

To address antibody endpoints in Part B, the analysis will descriptively summarize binding and neutralization response positivity call rates and test superiority of the frequency of differential memory B cell binding and of magnitude and breadth of the IgG

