binding Ab response to a panel of gp120 proteins and of the neutralization of tier 1 and tier 2 panels of HIV-1 viruses. Each analysis will be conducted separately for each of 2 pooled comparisons (additive vs sequential, pooling over groups with and without mosaic DNA: Groups 5 and 6 combined vs Groups 7 and 8 combined; effect of mosaic DNA, pooling over groups receiving additive and sequential proteins: Groups 5 and 7 combined vs Groups 6 and 8 combined), and for each of 6 pairwise comparisons among these groups using a two- sided Wilcoxon rank sum test with 5% type-I error rate per pooled comparison and a 5%/6 type-I error rate per pairwise comparison. The sample size of 20 vaccinees per group will give 80% power to detect a true difference of 1.63 standard deviations (SDs) between the mean non-zero responses and 90% power to detect a true difference of 1.81 SDs for the pairwise comparisons. Using the mean and SD values from the HVTN 088 trial, the difference of 1.63 SDs translates to a difference of 0.637 units of  $\log_{10}$  binding magnitude; if 1 of the comparison groups has the same mean as was seen among non-negative values among vaccine recipients in the HVTN 088 trial (4.06 units), then after incorporating the expected 6% zero-valued (negative responder) measures, this corresponds to observing an increase or decrease in the overall mean from 3.609 in group 1 to 4.175 in group 2. The sample size of 40 vaccinees per pooled group will give 80% power to detect a true difference of 0.80 standard deviations (SDs) between the mean non-zero responses and 90% power to detect a true difference of 0.90 SDs (these 2 are each conducted at a 5% alpha level). Using the mean and SD values from the HVTN 088 trial, the difference of 0.80 SDs translates to a difference of 0.313 units of  $\log_{10}$  binding magnitude; if 1 of the comparison groups has the same mean as was seen among non-negative values among vaccine recipients in the HVTN 088 trial (4.06 units), then after incorporating the expected 6% zero-valued (negative responder) measures, this corresponds to observing an increase or decrease in the overall mean from 3.722 in group 1 to 4.007 in group 2. These calculations assume a 10% loss-to-follow-up rate and the (94%) response rate observed in the HVTN 088 vaccine recipients. The same approach will be used to test superiority of the magnitude of the IgG binding Ab response to each individual gp120 antigen in the binding panel.

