To test for differences among the vaccine arms in Part A and separately in Part B, first a Kruskal-Wallis rank test or an F-test (depending on the normality assumption) will be used to test for overall differences. Secondly, if the overall test is significant at the 2-sided 0.05 level, then individual tests comparing the 2 adjacent pairs of vaccine arms (Part A) and all 6 pairs of 4 vaccine arms (Part B) will be done unless pre-specified. If rank-based tests are used then the tests will be inverted to construct Hodges-Lehmann point estimates and 2-sided  $(1-0.05/k) \times 100\%$  CIs about the differences in location centers of the  $k = 2$  (Part A) or  $k = 6$  (Part B) pair-wise comparisons of vaccine arms. If actual-value tests are used then the Dunnett's procedure will be used to construct simultaneous confidence intervals about the pairs of mean differences for the many-to-one comparisons [62] when multiple vaccine arms are each compared with 1 common control arm. When all pair-wise comparisons between the multiple vaccine arms are of interest, the Tukey procedure [63] will be used. If only specific comparisons between pairs of the multiple vaccine arms are of interest, the Holm-Bonferroni procedure will be used. An appropriate data transformation (eg,  $\log_{10}$  transformation) may be applied to better satisfy assumptions of symmetry and homoscedasticity (constant variance). Significance of the differences between pairs will be evaluated using 2 procedures, first based on whether the simultaneous 95% CIs exclude zero and secondly based on whether the nominal (unadjusted) 95% CIs exclude zero.

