### 6.4.4.5 Analysis of multiplexed immunoassay data

When a small panel of analytes (eg,  $\leq 5$ ) is being assessed in a multiplexed immunoassay, the analysis of response rates and response magnitudes will be evaluated and compared as described under the general approach. Details for calculating a positive response and response magnitude will be provided in the SAP. When a larger panel is being assessed, 2 approaches may be considered to evaluate the magnitude and breadth of these responses. First, Magnitude–Breadth (M-B) curves maybe employed to display individual- and group-level response breadth as a function of magnitude. Response breadth of neutralizing antibodies is defined as the average of the  $\log_{10}$  NAb titer over the panel of isolates, where titers that are below the limit-of-detection are set to half of that limit. Response breadth of binding antibodies is similarly defined as the average of the response over the panel of antigens. Two choices are to compare the M-B curves among vaccine arms, as follows: a non-parametric Wilcoxon rank sum test on the subject-specific area-under-the M-B curve (AUC M-B) or a Kolmogorov-Smirnov type test on the 2 group-average M-B curves. Simulations can be used to obtain 2-sided p-values for the latter test. Second, a weighted-average score-like variable may be constructed to account for the correlations between analytes as an integrate magnitude of responses to multiple analytes. Similar group comparison methods described in the first approach may be adopted. Details of either approach will be described in the SAP.

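### For floor-heavy assay readouts, the interval rule for rank-based pairs can contradict the Wilcoxon test on which the comparisons are powered

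*Combined protocol and SAP*

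**What the plan says.** Section 6.4.4.1 (General approach) starts with an overall Kruskal-Wallis or F-test, chosen on normality, and then compares pairs of vaccine arms: 2 adjacent pairs in Part A, all 6 pairs in Part B. On the rank route, "then the tests will be inverted to construct Hodges-Lehmann point estimates and 2-sided" intervals at level 1 - 0.05/k are formed, with k = 2 or 6. The decision rule is "Significance of the differences between pairs will be evaluated using 2 procedures, first based on whether the simultaneous 95% CIs exclude zero". The other procedure repeats this check without the multiplicity adjustment, so both rest on intervals. No p-value is named as deciding a pair.

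Section 6.1.2 describes the same comparisons as tests. Part A uses a two-sided "Wilcoxon rank sum test with 5%/2 type-I error rate per comparison". Part B, also two-sided, uses a "Wilcoxon rank sum test with 5% type-I error rate per pooled comparison and a 5%/6 type-I error rate per pairwise comparison", and covers binding as well as tier 1 and tier 2 neutralization panels.

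Section 6.4.4.5 says how low neutralization titers are scored: "titers that are below the limit-of-detection are set to half of that limit". It also names the Wilcoxon test on each participant's area under the magnitude-breadth curve (AUC) as one option.

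The supplied text does not say how ties are treated when the test is inverted, or which result governs if the test and the interval disagree.

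**The concern.** Reading a test from its inverted interval is harmless for continuous data that differ by a shift. It is not harmless with a large point mass. Every titer below the limit receives the same value, so a floor value in one arm minus a floor value in the other is exactly 0. If there are enough such pairs, the Hodges-Lehmann limit lands on 0, however small the Wilcoxon p-value is.

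The rank route is also the one taken when normality fails, which is what floor-heavy data produce. The most exposed endpoints are single-isolate neutralization titers, and a panel AUC when many participants are negative to every isolate. In the macaque neutralization table (Section 4.8.1, Figure 4-8), 12 of 12 animals were below 20 for the tier 2 CH505 virus and 10 of 12 for D.57128. CH505 TF is an isolate planned for the human assay (Section 10.5.2).

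At stake is the quantitative pairwise conclusion: the written rule can report no significant difference where the planned test, at the same level, finds one.

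**Working it through.** **1. The plan's own power.** Inputs from Section 6.1.2: 12, 20 and 40 per group; 10% missing, so 11, 18 and 36 evaluable; 94% non-zero; mean 4.06 and SD 0.391 log10 among non-zero values. The stated overall means imply fixed non-zero counts: 4.06 × 10/11 = 3.691, 4.06 × 16/18 = 3.609, 4.06 × 33/36 = 3.722. Simulating a tie-corrected Wilcoxon test on that basis (20,000 datasets per case) gives:

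| Comparison | Level | Effects (SD) | Stated power | Simulated power |
|---|---|---|---|---|
| Part A pair | 5%/2 | 1.81 / 2.04 | 80% / 90% | 80.1% / 89.8% |
| Part B pair | 5%/6 | 1.63 / 1.81 | 80% / 90% | 79.9% / 89.7% |
| Part B pooled | 5% | 0.80 / 0.90 | 80% / 90% | 80.6% / 89.6% |

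The stated figures reproduce. In the same simulations the interval rule loses 0, 1.5 and 1.8 percentage points at the 80% effects. With this few zeros the rule is sound.

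**2. When the interval can exclude 0.** The closed interval runs between order statistics of the m × n between-arm differences, at rank C ≈ mn/2 - z√(mn(m+n+1)/12). For 18 v 18 (324 differences) the formula gives 78.6 at 5%/6; the exact rank is 80. At 5% the exact rank is 100. The lower limit is above 0 only if fewer than C differences are at or below 0:
- 5%/6: at least 324 - 79 = 245 of 324 (76%) must strictly favour one arm.
- 5%: at least 324 - 99 = 225 of 324 (69%).

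Once floor-floor pairs alone reach C, the interval cannot exclude 0 in either direction. In a Part B pair, 9 of 18 at the floor in each arm gives 9 × 9 = 81, against 80. In a Part A pair (11 v 11, exact rank 27 of 121), 6 and 5 at the floor give 30.

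**3. Two worked cases, 18 v 18.**
- 0/18 v 13/18 responders: 18 × 5 = 90 zero differences. Since 90 ≥ 80, the simultaneous interval starts at 0; since 90 < 100, the nominal interval does exclude 0. Wilcoxon p = 0.00002.
- 0/18 v 11/18 responders: 18 × 7 = 126 zero differences, above both ranks, so both order-statistic intervals start at 0. Wilcoxon p = 0.00013.

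**4. Power with many floor values.** The documents give no human floor shares. Assumption: responder rates as shown, with responders normal at 1 log10 above the floor, SD 0.4. With 18 per arm at 5%/6, to within about a point:

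| Responder rates | Wilcoxon | Order-statistic interval |
|---|---|---|
| 5% v 50% | 66% | 1% |
| 10% v 60% | 70% | 5% |
| 30% v 80% | 53% | 21% |

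The second procedure does not repair this: for 10% v 60% at nominal 5%, about 90% v 15%. In Part A (11 per arm, 5%/2, 10% v 60%) the figures are about 55% v 8%, with responders in the second arm also 0.5 SD higher. With no true difference, 18 per arm, half the values at the floor and nominal 5%, Wilcoxon rejects 4.9% of the time and the interval rule 0.3%.

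**5. Dependence on software.** R's wilcox.test with a numerically inverted interval (18 per arm, 5%/6, 600 datasets per case) excluded 0 in about 23%, 47% and 51% of datasets for the three rows above, with Wilcoxon rejecting in 68%, 69% and 55%. In a 10% v 60% run, 41% of all datasets had an interval that excluded 0 by less than 0.001.

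**The case against.** The strongest reply is that the plan has other routes to such differences, and most of it stands.

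- Section 6.4.4.1 compares Part B response rates between any two vaccine arms by Barnard or Fisher tests at 0.05. Fisher's power in the three scenarios above is about 84%, 86% and 83%, and for 0/18 v 13/18 its p-value is 0.000007. A reader might infer that a regimen neutralizing in most recipients would be reported as no different from one that induces nothing. The documents do not support that.
- The same section offers a two-part test with a permutation p-value for dichotomized assays. This would avoid the problem, but it applies only if a mixture model is judged the best summary, and no criterion is given.
- Sections 6.4.4.2 and 6.4.4.3 handle neutralization AUC by Dunnett screens, an F-test with Fisher's least significant difference, and a distributional statistic with Holm-Bonferroni. None uses a Hodges-Lehmann interval. Section 6.1.2 does plan Wilcoxon tests for the tier 1 and tier 2 panels, but that overlap does not show that the interval rule governs them.
- Ties may be rarer than feared. A panel AUC ties at the floor only when every isolate is negative, and 12 of 12 macaques were above 20 for CH505.w4.3, a variant in the planned autologous panel. Where all values are at the floor, Wilcoxon finds nothing either. T-cell magnitudes are background-subtracted (Section 6.4.4.4) with no stated floor.
- A strict inversion rejects the point 0 whenever the test does. But values just above 0 remain in the set, so the reported closed limit is still 0. Section 6.4 allows SAS and R for primary analyses and adds StatXact for others; a decision that turns on a limit of 0 or a hair above it is not a specified rule.

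**Conclusion.** The point holds in a limited form. As written, the rule for rank-based pairs can contradict the Wilcoxon test on which the plan is powered, when roughly half or more of the values are at the floor. At assumed responder rates of 10% v 60% in a Part B pair, the loss is from about 70% to 5% with order-statistic limits, and to about 47% with R's inversion. These sizes rest on assumed floor shares and responder distributions.

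What is lost is the quantitative pairwise conclusion, not every route to detection. Binding endpoints lose at most about 2 points, and the mean-based neutralization AUC rules are untouched. The rate-test safeguard is stated for the aims of Part B only. This is a defect of wording that should be corrected before unblinding; it does not call the design into question.

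**What to change.** In Section 6.4.4.1, for rank-based pairs:

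1. Declare significance from the tie-corrected or permutation Wilcoxon p-value at the stated level: 5%/k for the first procedure and nominal 5% for the second.
2. Keep the Hodges-Lehmann estimate and interval for estimation only, and state the tie handling and software used to compute them.
3. For floor-heavy assays, report the already planned response-rate difference beside the Hodges-Lehmann estimate. The Mann-Whitney probability, counting ties as one half, is an optional addition.

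The cost is SAP wording only: no new data and no change to sample size or alpha. A significant p-value may then appear beside an interval that touches 0, so a sentence explaining why should accompany such results.

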If a substantial amount of immunogenicity data are missing for an endpoint (at least 1 value missing from more than 20% of participants), then using the methods that require the MCAR assumption may give misleading results. In this situation, analyses of the immunogenicity endpoints at a specific timepoint will be performed using parametric generalized linear models fit by maximum likelihood. These methods provide unbiased estimation and inferences under the parametric modeling assumptions and the assumption that the missing data are missing at random (MAR). MAR assumes that the probability of an observation being missing may depend upon the observed responses and upon observed covariates, but not upon any unobserved factors. Generalized linear models for response rates will use a binomial error distribution and for quantitative endpoints, a normal error distribution. For assessing repeated immunogenicity measurement, linear mixed effects models will be used. If the immunological outcomes are left- and/or right-censored, then the linear mixed effects models of Hughes [66] will be used, because they accommodate the censoring. In addition, secondary analyses of repeated immunogenicity measurements may be done using weighted GEE [67] methods, which are valid under MAR. All of the models described above in this paragraph will include as covariates all available baseline predictors of the missing outcomes.

Some “resource-intensive” immunogenicity endpoints are only measured in subset of participants, eg, immunogenicity endpoints based on mucosal samples. For such endpoints, exploratory analyses will be conducted to assess the correlation of participant characteristics measured in (nearly) all subjects with the resource-intensive endpoints. For example, if the same assay is performed on blood and mucosal samples, then a scatterplot and Spearman rank correlation coefficient ( $r$ ) will be used to assess the correlation of responses. If at least moderate correlations exist (eg,  $r \geq 0.3$ ), then the semiparametric efficient analysis method of Rotnitzky and Robins [68] will be used (described in Gilbert, Sato et al. for application to vaccine studies [69]) to estimate the mean of the resource-intensive endpoint for each group and to compare means between groups.

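### Above 20% missing data, the single-timepoint GLM protects against less than the plan's MAR statement claims, chiefly for the Part B day 500 contrast

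*Combined protocol and SAP*

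**What the plan says.** Section 6.4.4.1 (General approach) uses complete-case methods while no more than 20% of participants have missing values. The other branch opens when there is "at least 1 value missing from more than 20% of participants". Then "analyses of the immunogenicity endpoints at a specific timepoint will be performed using parametric generalized linear models fit by maximum likelihood", with binomial error for response rates and normal error for quantitative endpoints.

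The property claimed is: "These methods provide unbiased estimation and inferences under the parametric modeling assumptions and the assumption that the missing data are missing at random (MAR"). MAR is defined so that "the probability of an observation being missing may depend upon the observed responses and upon observed covariates, but not upon any unobserved factors".

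Three further sentences bear on the point:

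- Covariates: "All of the models described above in this paragraph will include as covariates all available baseline predictors of the missing outcomes". No postvaccination response is named as a covariate.
- Repeated data: "For assessing repeated immunogenicity measurement, linear mixed effects models will be used", with a version for censored outcomes.
- Optional: "secondary analyses of repeated immunogenicity measurements may be done using weighted GEE [67] methods, which are valid under MAR".

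The Part B primary immunogenicity timepoints are day 238 and day 500, two weeks after the fourth and sixth vaccinations (Sections 5.4 and 10.3). The footnotes on immunogenicity assays commit to M0 (binding antibody) and M4.5 in Part A (Appendix I), and to M0 (binding antibody), M8.5 and M16.5 in Part B (Appendix J).

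**The concern.** The MAR definition covers the case where a participant's day 238 result influences whether a day 500 result exists. A GLM for day 500 alone never sees the day 238 result, so it cannot correct for that. The models that could, the mixed model and the weighted GEE, are attached to repeated measurement, and the second is optional and secondary. Neither is assigned to the contrast at one timepoint.

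This branch is entered only once the plan itself regards missingness as serious. If the day 500 comparison of regimens is then reported as unbiased under MAR, readers will credit it with a protection it only partly has.

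**Working it through.** **1. What each likelihood uses.** Let y1 be the day 238 response, y2 the day 500 response, x the baseline covariates, and r = 1 if y2 is observed.

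- Single-timepoint GLM: the log-likelihood is Σ r·log f(y2 | arm, x). A participant with r = 0 contributes nothing. The fit targets f(y2 | arm, x) only if P(r = 1) depends on arm and x alone. If it also depends on y1, and y1 is correlated with y2 given arm and x, the observed y2 are a selected sample.
- Joint model: Σ log f(y1 | arm, x) + Σ r·log f(y2 | y1, arm, x). Conditioning on y1 removes that selection, so the MAR statement holds.

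**2. Yardstick from the plan.** Section 6.1.2 gives 40 per pooled group 80% power at 0.80 SD and 90% at 0.90 SD (two-sided Wilcoxon at 5%, 10% loss, 94% non-zero). Simulation with 36 evaluable per group, 33 of them non-zero, gives 80.1% and 90.0%; 4.06 × 33/36 = 3.722 matches the stated overall mean. Biases below can be read against 0.80 SD.

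**3. Size of the GLM bias.** The documents do not give the following, so they are assumptions: missing fraction m at day 500; day 238/500 correlation 0.7; a baseline covariate correlated 0.2 with both responses; no true difference. Low-responder loss means that a fraction 2m of those below the day 238 median are missing and none above it. The mean of a half-normal variable is √(2/π) = 0.798.

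- Shift in day 238 mean among those retained: 0.798 × m/(1 − m).
- Shift in day 500 mean after baseline adjustment: approximately (0.7 − 0.2²) × that = 0.66 × that.
- m = 0.25: 0.798 × 0.25/0.75 = 0.266; × 0.66 = 0.176 SD. Opposite tails double it: 0.35 SD.
- m = 0.10: 0.798 × 0.10/0.90 = 0.089; × 0.66 = 0.059 SD. Opposite tails: 0.117 SD.
- Same rule in both groups: the shifts cancel.

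Simulation agrees. Type I error of the GLM test:

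| Missingness at day 500 | Bias (SD) | 40 per group, 5% | 20 per arm, 5%/6 (nominal 0.83%) |
|---|---|---|---|
| 25%; low responders lost in one group, random loss in the other | 0.18 | 11% | 1.6% |
| 25%; opposite tails lost | 0.35 | 29% | 4.2% |
| 25%; same rule in both groups | about 0 | 5.9% | – |
| 10%; one group only | 0.06 | 5.4% | – |
| 10%; opposite tails | 0.11–0.12 | 8.1% | – |

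A separate run gave 1.5% and 4.7% in the last column. Against 0.80 SD, the first two biases are 0.18/0.80 = 23% and 0.35/0.80 = 44%. The joint likelihood of days 238 and 500 has bias near zero in the 25% scenarios with differing loss.

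**4. Other assumptions, with a true difference of 0.80 SD.** With 30% missing, a log-odds slope of 1.5 per SD, covariate correlation 0.4 and day 238/500 correlation 0.3, 0.6 or 0.8, the baseline-adjusted GLM gives:

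- Missingness depends on baseline, in opposite directions by arm: bias at most 0.007 SD, against 0.26–0.27 SD without the covariate.
- Depends on day 238, same rule in both arms: −0.03, −0.07, −0.10 SD.
- Depends on day 238 in one arm only: 0.04, 0.15, 0.21 SD.
- Opposite directions by arm: 0.10, 0.30, 0.43 SD.

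Joint likelihood bias is 0.006 SD or less in absolute value throughout.

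**5. How often the branch opens.** Section 6.1 plans for 10% missing. Counted at one timepoint, the chance that more than 20% are missing is about 0.2% or less with 80 or 90 participants. Counted as missing either of two timepoints, and assuming independence, 1 − 0.9² = 19% are affected and the chance is about 35%. The section does not say which count applies.

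**The case against.** A reader might infer that the stated protection does not exist at all. The documents do not support that. The paragraph requires all available baseline predictors in every model, and step 4 shows that this removes a 0.26–0.27 SD bias when missingness depends on baseline.

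A reader might also take every primary endpoint to be exposed. In Part A the only committed assays are M0 (binding antibody) and M4.5, so there is normally no earlier postvaccination response to ignore.

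The assignment of models can be contested. Part B's primary endpoints are measured at two visits, and neutralization titers have a detection limit, so one could argue that the mixed model or its censored version already applies. That is possible, but the text gives contrasts at a specific timepoint to the GLM and does not say that the mixed model supplies them.

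The strongest objection concerns size, and most of it stands. The trial is double-blind, and the causes of missing data listed (early termination, shipping, cell viability, high background) suggest no arm-specific mechanism. The same rule in both groups gives essentially no bias under the null. The 25% rate is 2.5 times the planned 10%. If the branch opens because misses are counted over two visits, day 500 loss may be near 10% and the bias only 0.06–0.12 SD. None of this makes the MAR sentence correct as written.

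**Conclusion.** The concern holds in a limited form. The single-timepoint GLM is valid when missingness depends on arm and the modelled baseline covariates. It does not have the stated property when missingness depends on an earlier postvaccination response, which the plan's own definition of MAR allows. This follows from the likelihood and needs no assumed values.

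The practical scope is essentially the Part B day 500 contrast. The illustrated sizes, 0.18 SD with 11% type I error and 0.35 SD with 29%, require 25% missing, correlation 0.7 and loss patterns that differ between groups; the second is an extreme case. They show what the branch could let through and do not forecast this trial. Under the null, substantial bias needs missingness that relates to the day 238 response differently in the groups compared.

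**What to change.** For the branch above 20% in Part B, state that the day 500 arm contrast comes from the linear mixed model already in the plan, fitted to days 238 and 500 with arm-by-visit means, unstructured covariance and the baseline covariates. Use the censored version where relevant. Limit this to endpoints and arms assayed at both visits: Section 6.4.4.2 does not plan tier 2 neutralization for regimens that fail the tier 1 screen, so a joint tier 2 model may not cover every arm.

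Where no earlier postvaccination response is assayed, as is normal in Part A, keep the GLM and restrict the claim to missingness that depends on arm and the modelled baseline covariates. Apply the same restriction to response rates, which the linear mixed model does not cover, unless the weighted GEE already listed is assigned to them. State also whether the 20% is counted at one timepoint or across visits.

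The cost is a few sentences in the SAP. The model and both visits' assays are already planned, so no added participants, samples or assays are needed.

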### 6.1.2 Sample size calculations for immunogenicity

To address the humoral immunogenicity endpoints, the analysis will compare the area under the magnitude-breadth curve of the IgG Env binding Ab response, and will compare the frequency of memory B cells that bound to gp120CH505 TF but not to gp120CH505 TF  $\Delta$ 371, 2 weeks after the third (Part A) or fourth and sixth (Part B) vaccinations with CH505TF gp120. To estimate power, binding magnitude-breadth data were simulated assuming that the proportion of non-zero responses was 0.94 in both comparison groups. This is based on pilot data for the IgG binding Ab response in HVTN 088. For these calculations, non-zero responses, modeled on the  $\log_{10}$  scale, were drawn from a normal distribution. The mean non-zero response in group 1 was set to 4.06. This was the mean non-zero response in the HVTN 088 vaccine arm T2 (the treatment arm for vaccine naïve participants). The standard deviation (SD) of the non-zero response was set to 0.391 for both groups; this was the SD of the non-zero response in the HVTN 088 vaccine arm.

The differential binding rate is the fraction of class memory B cells that have the property of binding the two protein hooks in a differential manner (defined by flow gating). In the assay, two measurements are made simultaneously: binding to the transmitted founder CH505 virus, and binding to the  $\text{I}\Delta 371$  variant. Each of these yields a measurement of the proportion of memory B cells that bind to a target virus. While the primary interest is in the differential binding to these two viruses, which is the difference of these proportions, we will also evaluate each measure separately to further describe and explore the relationship between these measures under the scenarios represented by the arms of this trial.

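### Once more than 20% of participants have missing data, response rates move to an ordinary maximum-likelihood binomial model, with no rule for an arm at 0% or 100% responders, where its log-odds estimate and Wald inference break down.

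*Combined protocol and SAP*

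**What the plan says.** All of the following is in the combined protocol and SAP.

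- **Default methods (section 6.4.4.1).** Crude response rates get 95% score intervals. For the aims of Part B, rates are compared between vaccine arms and pooled groups by Barnard or Fisher exact tests.
- **Trigger.** The default gives way when there is "at least 1 value missing from more than 20% of participants".
- **Fallback.** Analyses at a specific timepoint then use "parametric generalized linear models fit by maximum likelihood". On the distribution: "Generalized linear models for response rates will use a binomial error distribution and for quantitative endpoints, a normal error distribution".
- **Covariates.** "All of the models described above in this paragraph will include as covariates all available baseline predictors of the missing outcomes".
- **Not stated.** The missing-data paragraphs give no link function, effect measure, interval method or test, and no rule for an arm with all or no responders. They do not defer these points to the SAP, although section 6.4.4.1 does so for other choices.
- **A planning rate.** Section 6.1.2 simulates binding-antibody data "assuming that the proportion of non-zero responses was 0.94 in both comparison groups", and states: "These calculations assume a 10% loss-to-follow-up rate and the (94%) response rate observed in the HVTN 088 vaccine recipients".

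**The concern.** The default methods remain valid when every participant in an arm responds, or none does. The replacement, fitted in the usual way, does not. With a logit link and a term for each arm, an arm with no non-responders drives its coefficient to infinity. Software reports a very large coefficient with an enormous standard error, and the Wald interval and p-value carry no information.

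The switch takes place when arms have shrunk to about 9–10 (Part A) or 15–16 (Part B), sizes at which a boundary arm is common if the true rate is near 0% or 100%. The required baseline covariates can only add to separation. A clear difference could be reported as null because the method changed. Otherwise a replacement would have to be chosen after seeing which arms are at the boundary. The endpoint most clearly exposed is the CD4+ T-cell response rate by ICS, a named secondary endpoint in both parts (sections 5.2 and 5.5).

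**Working it through.** **Inputs.** Vaccine arms: 3 of 12 in Part A and 4 of 20 in Part B, with pooled Part B groups of 40 (Table 3-1, section 6.1.2). Response rate 0.94 (section 6.1.2). Trigger above 20% and planned missingness 10% (sections 6.1 and 6.4.4.1).

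**Reproducing the plan's figures.** Simulating the plan's model for Part A (94% non-zero, normal with mean 4.06 and SD 0.391, difference 1.81 SD, two-sided Wilcoxon at 0.025, 11 observed per arm from 12 × 0.9 = 10.8) gives 79% power against the stated 80%. The zero-event formula used below, (1 − p)^n, reproduces Table 6-1 at a 4% rate: 0.96^12 = 61.3% and 0.96^20 = 44.2%.

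**Step 1: arm sizes when the branch applies.** The smallest loss above 20% is 8 of 36 vaccinees in Part A (28 left: 10, 9, 9) and 17 of 80 in Part B (63 left: 16, 16, 16, 15; pooled 32 and 31). At 25% missing the arms are 9 and 15, pooled 30.

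**Step 2: chance of a boundary arm at 94%.** One arm of m is all responders with probability q = 0.94^m; at least one of k arms with probability 1 − (1 − q)^k.

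| Comparison | m | q | k | At least one at 100% |
|---|---|---|---|---|
| Part A, any arm | 10 / 9 | 0.539 / 0.573 | 3 | 90% / 92% |
| Part B, any arm | 16 / 15 | 0.372 / 0.395 | 4 | 84% / 87% |
| Part B, one pair | 16 / 15 | 0.372 / 0.395 | 2 | 61% / 63% |
| Part B, pooled contrast | 32 / 31 | 0.138 / 0.147 | 2 | 26% / 27% |

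With 30 per pooled group the last figure is 29%. As a check, logit-link binomial models with one term per arm were fitted to 1,000 simulated data sets per part. The divergence rate equalled the boundary-arm rate: 91.5% in Part A (9 per arm) and 83.4% in Part B (16 per arm).

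**Step 3: dependence on the rate.** Same formula, any arm:

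| True rate | Part A (10 / 9 per arm) | Part B (16 / 15 per arm) |
|---|---|---|
| 94% | 90% / 92% | 84% / 87% |
| 90% | 72% / 77% | 56% / 60% |
| 80% | 29% / 35% | 11% / 13% |

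The calculation is symmetric: a true rate of 6% gives the same chance of an arm at 0%.

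**Step 4: what the model returns.** Take 16/16 against 9/16, no covariates, logit link. The arm coefficient is about −22.3 with standard error about 12,000 and Wald p = 0.999. On the same data Fisher gives p = 0.007 and Barnard p = 0.003. The likelihood-ratio statistic is 11.69 on 1 df, p = 0.0006. The risk difference is 1 − 9/16 = 44 points, with a profile-likelihood 95% interval of about 21 to 68 points.

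**Step 5: how often the branch is reached.** If each participant independently has a 10% chance of missing data, the binomial probability of exceeding 20% is about 2% in Part A (N = 36 or 42) and 0.1–0.2% in Part B (N = 80 or 90). Part B has two primary timepoints. If both count towards the trigger and are independent (an assumption), the per-participant chance is 1 − 0.9² = 19% and the branch is reached about 35% of the time.

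**The case against.** Several objections have force.

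- **The plan names neither a logit link nor Wald inference.** A reader might infer that the fallback returns no estimate or interval at all. The documents do not support that. The fitted probability is simply 1, the risk difference is finite, and likelihood-ratio inference works in the example. What stands is that the plan specifies none of these. The canonical logit with Wald output fails, and under an identity link the Wald standard error in a boundary arm collapses to zero.
- **The 94% belongs to another analysis.** It is the proportion of non-zero binding-antibody responses, used for power on magnitude. Section 6.1.2 has binding positivity calls summarized descriptively, section 6.4.4.1 names exact tests only for Part B, and no expected CD4+ rate is given. The frequencies therefore need the range in step 3.
- **The primary neutralization results are untouched.** Because tier 2 response rates may be near zero, a reader might infer that tier 2 neutralization fails too. Sections 6.4.4.2 and 6.4.4.3 analyse magnitude-breadth AUC or curves, which are quantitative. Only a supplementary tier 2 response rate could be affected.
- **It is not most data sets for every comparison.** One boundary arm leaves contrasts among the other arms estimable, and pooled contrasts are affected in a minority.
- **The branch is rarely reached at the planned 10% missingness.** This is correct, unless timepoints are counted together.

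The covariate requirement makes separation more frequent, but the number of covariates is not given, so no figure is attached to it. None of these objections supplies the missing rule.

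**Conclusion.** The point holds as a gap in a contingency analysis that should be closed. The stated fallback swaps boundary-safe methods for one whose usual logit and Wald output is unusable when an arm is at 0% or 100%.

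Once the branch applies at 20–25% missing, and if response calls run at 94%, most Part A and Part B multi-arm fits and most individual pairs meet this problem, as do about a quarter of pooled Part B contrasts. At 80% it is a minority everywhere. These figures assume independent participants, even loss across arms and no covariates.

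The exposure is to response-rate endpoints, chiefly the secondary CD4+ T-cell response rate. The conclusion does not depend on the 94%: any endpoint with rates close to either extreme behaves the same way at these arm sizes.

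**What to change.** In the missing-data paragraph of section 6.4.4.1, and in the SAP, for response rates only:

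1. Name the link function and the effect measure to be reported.
2. Replace ordinary maximum likelihood with Firth penalized likelihood, using profile penalized-likelihood intervals and penalized likelihood-ratio tests.
3. Keep the baseline predictors of the missing outcomes as covariates, since the missing-at-random argument relies on them.
4. Report the default score intervals and exact tests alongside, as a complete-case sensitivity analysis.

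In the 16/16 against 9/16 example, with no covariates, Firth's method amounts to adding one half to each cell. The log odds ratio is ln[(16.5/0.5) / (9.5/7.5)] = ln 26.05 = 3.26, which is finite.

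Multiple imputation followed by the default tests is less ready to use: a logistic imputation model can itself separate, and Barnard p-values have no direct pooling rule.

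The cost is wording, with software available in SAS and R, both already named in section 6.4. The downside is slight shrinkage toward no difference. The change should be made before unblinding, so that the method is not chosen after seeing which arms are at the boundary.
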